8.6 Safety Oversight

Safety oversight will be under the direction of the PBRS MM and the Sponsor's designated Drug Safety Unit. The PBRS MM reviews and evaluates safety and/or efficacy data on an ongoing basis to ensure the safety of patients and the validity and integrity of data. The PBRS MM reviews SAEs, deviations, Interim analysis and final report forms, and can make the following determinations, Accepted, Acceptable with Corrective Action and Tabled. The PI shall provide a statistical report of the study's progress and summary of adverse events and deviations based on the phase of the study and the associated risk of the study as often as is applicable.

9 CLINICAL MONITORING

Clinical site monitoring is conducted to ensure that the rights and well-being of human subjects are protected, that the reported trial data are accurate, complete, and verifiable, and that the conduct of the trial is in compliance with the currently approved protocol/amendment(s), with good clinical practice (GCP), and with applicable regulatory requirements.

The PI and the Clinical Research Coordinator assigned to the case will be responsible for collecting all study data and maintaining all study-related documents, including the Investigator's Study File (ISF) and patient Case Report Forms (CRFs). All CRF entries will be made into paper CRFs provided by the study site and will be verified by the PBRS CRA against both paper source documentation and electronic medical records (EMR). The patient CRFs will be secured in a locked office in the Cutaneous Research Department. The review of medical records will be done in a manner to assure that patient confidentiality is maintained.

Regulatory documents will be reviewed and CRFs will be monitored by the PBRS Clinical Research Associate (CRA) according to PBRS Standard Operating Procedures (SOPs). Monitoring will be performed regularly for accuracy, completeness, and 100% source data verification, validation of appropriate informed consent process, reporting of SAEs, and adherence to the protocol, Good Clinical Practice (GCP) guidelines, and all applicable regulatory requirements.

To ensure adherence to the protocol, monitoring reports will be submitted to the sponsor according to the timelines specified in the PBRS Global Monitoring Plan.

10 STATISTICAL CONSIDERATIONS

10.1 Statistical and Analytical Plans

The statistical and analytical plan was developed to assess safety in six patients.

10.2 Statistical Hypotheses

IFX-Hu2.0 may be given safely to patients with unresectable stage III/IV melanoma.

10.3 Analysis Dataset(s)

Safety Analysis Dataset: the subset of participants for whom safety analyses will be conducted (e.g., participants who took at least one dose of Investigational Product).

10.4 Description of Statistical Methods

10.4.1 General Approach

This is a feasibility study that is designed to evaluate the safety and the feasibility of IFx-Hu2.0 as a monotherapy in preparation for a combination trial with Keytruda® (pembrolizumab) for the treatment of unresectable stage III/IV metastatic melanoma. Safety will be assessed and reported based upon CTCAE v5.0 criteria. Feasibility will be defined as the ability to treat at least five of the six patients enrolled without dose-limiting toxicity.

The secondary endpoints consist of the objective response rate and immune response assessments. Responses will be determined using standard criteria. Other secondary endpoints will be exploratory laboratory correlative endpoints of interest. This will include immunology assessments to include but not limited to: quantity of effector T cells in the circulation and expression of the Emm55 protein within the tumor tissue. The data analysis of exploratory laboratory correlative endpoints will be descriptive. All study results will be preliminary and exploratory in nature due to the relatively small sample size of the trial.

The data analysis will mainly be descriptive. The intention-to-treat approach will be used for response to treatment data analysis of this trial. Patients who are lost to follow-up or drop out of the study for any reason prior to their scheduled Final Study Visit will be censored for any time-to-event type of endpoints at the time of their last patient contact if no relevant event has occurred by then. The overall response (CR+PR) rate will also be summarized.

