ECG	Electrocardiography
ECOG	Eastern Cooperative Oncology Group
eCRF(s)	electronic Case Report Form(s)
E. coli	Escherichia coli
EtBr	Ethidium Bromide (DNA stain)
FTA	Fluorescent Treponemal Antibody
GAPDH	Glyceraldehyde 3-Phosphate Dehydrogenase
GCP	Good Clinical Practice
HBV	Hepatitis B Virus
HCV	Hepatitis C Virus
HEK293T	Human Embryonic Kidney cells
HIV	Human Immunodeficiency Virus
HLA	Human Leukocyte Antigen
HTLV	Human T Lymphotropic Virus 1 & 2
ICH	International Conference on Harmonisation
ICMJE	International Committee of Medical Journal Editors
IHC	Immunohistochemistry
IFx-Hu2.0	pAc/emm55 DNA plasmid combined with in vivo-jetPEI® in the presence of glucose
INF γ	Interferon Gamma

IRB	Institutional Review Board
LDH	Lactate Dehydrogenase
LTF	Lost to Follow Up
MCB	Master Cell Bank
MHC	Major Histocompatibility Complex
MM	Medical Monitor
NED	No Evidence of Disease
OD	Optical Density
ORR	Overall (Objective) Response Rate
OS	Overall Survival
pAc/ emm55	DNA plasmid encoding the emm55 gene
pAc/empty	pAc/ emm55 DNA plasmid without the emm55 gene
PBRS	Peachtree Bioresearch Solutions, Inc.
PBS	Phosphate Buffered Saline
PCR	Polymerase Chain Reaction
PD	Progressive Disease = ≥ 20% increase in tumor burden
PD-1	Programmed Cell Death Protein 1
PE	Phycoerythrin
PET	Positron Emission Tomography
PFS	Progression-Free Survival
PI	Principal Investigator
PT	Prothrombin Time
PR	Partial Response = ≥ 30% decrease in tumor burden
QC	Quality Control
RAB-AP01	Anti-Emm55 Rabbit Polyclonal Antibody
RECIST v1.1	Response Evaluation Criteria in Solid Tumors version 1.1
RPR	Rapid Plasmin Reagin
RTPCR	Reverse Transcriptase Polymerase Chain Reaction
SAE(s)	Serious Adverse Event(s)
SC	Subcutaneous
SCB	Starter Cell Bank
SEM	Standard Error of the Mean
SD	Stable Disease = % change in tumor burden is between -30% and +20%
SOP	Standard Operating Procedure
S. pyogenes	Streptococcus pyogenes
SumL	Sum of the Longest Diameters
TCR	T Cell Receptor
TE	10 mM Tris-Cl, pH 8.0, 1 mM Ethylenediaminetetraacetic acid
TEAE(s)	Treatment-emergent adverse event(s)
UP(s)	Unexpected Adverse Drug Experience
VCOG	Veterinary Cooperative Oncology Group
WCB	Working Cell Bank

STATEMENT OF COMPLIANCE

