4.2.2 Secondary Endpoints

The secondary endpoint consists of observing and monitoring objective response rates and, although not needed for the conclusion of this study, progression-free survival (PFS) will also be recorded when indicated. Patients who consent to additional injection cycles will be observed for toxicity over time.

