7.1.2 Standard-of-care Study Procedures

Subjects will receive IFx-Hu2.0 as a monotherapy at a single time point and will be assessed for a period of four weeks. Once the four-week period expires and the toxicity/safety assessments have been completed, these patients will transition into standard-of-care or clinical trial protocols as determined by the PI and the clinical team. If the patient comes off study, PFS will need to be censored, but the time to first progression will be obtained during subsequent follow-up with the patient's consent. If the patient has a response to therapy, the patient will have the option of continuing the study at three-week intervals at the discretion of the PI in consultation with the Sponsor. In this setting, PFS will be measured in the traditional way. Where feasible, as determined by PI, tumor biopsies and peripheral blood collections may be obtained on subsequent treatment cycles.

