7.3.4 Final Study Visit

(Week 4 Day 28 +/- 7 business days for Single Dose Cycle)

OR

(Week 21 +/- 7 business after the last dose for Multiple Dose Cycle)

- Record vital signs, results of physical examination
- Collect blood/urine for:
 - Hematology: CBC - hemoglobin, hematocrit, white blood cells (WBC) with differential count, platelet count; blood clotting tests: prothrombin time (PT), activated partial thromboplastin time (aPTT)
 - Biochemistry: CMP - glucose, calcium, albumin, total protein, sodium, potassium, CO₂, chloride, BUN, creatinine, total bilirubin, alanine aminotransferase (ALT), aspartate aminotransferase (AST), alkaline phosphatase (ALP), lactate dehydrogenase (LDH); thyroid tests: (TSH and FT4)
 - Urinalysis: UA with microscopic evaluation
 - Serum pregnancy test
 - Anti-double-stranded DNA (anti-dsDNA) antibody test
 - Anti-DNase B Titer, Serum
 - 40 mL of blood will be collected for research purposes in the laboratory of [name], including immune response evaluation.
- Tumor sample biopsy of injected lesion for histology and immune response assays
- Biopsy of non-target lesion (if applicable)
- Assessment and recording of ECOG Performance Status
- Assessment and recording of Tumor Burden (lesion measurements)
- Assessment and recording of Concomitant Medications
- Observation and recording of adverse or serious adverse events as defined by CTCAE v5.0
- CT as clinically indicated and/or PET scan (photographs may be utilized for melanoma confined to the skin)

Overall Survival Status: Long Term Follow-up

- On 11/16/2020 (\pm 4 weeks), the survival status and subsequent anti-cancer therapy since last being seen on trial will be obtained from the EMR. Subsequent therapies will be documented from the EMR for melanoma (immune-based therapy, chemotherapy, radiation, surgery) with clinical response if available.

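### Section 10.4.1 censors PFS at last patient contact, so time after the last tumour measurement can count as progression-free without having been observed

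*Combined protocol and SAP*

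**What the plan says.** Section 10.4.1 gives one censoring rule. It covers "Patients who are lost to follow-up or drop out of the study for any reason prior to their scheduled Final Study Visit", and such patients "will be censored for any time-to-event type of endpoints at the time of their last patient contact if no relevant event has occurred by then".

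PFS falls under that rule. Section 4.2.2 lists it with the secondary endpoints, in a minor role: "although not needed for the conclusion of this study, progression-free survival (PFS) will also be recorded when indicated".

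The list of abbreviations defines progression by measurement: "Progressive Disease = ≥ 20% increase in tumor burden". Lesion measurement is listed at screening, at the dosing visits, at the final visit ("Assessment and recording of Tumor Burden (lesion measurements", section 7.3.4) and at the early termination visit (7.3.5). For unscheduled visits the plan is inconsistent: the list in 7.3.6 has no lesion measurement, but the single-dose table in 7.3.7 marks tumour burden for that visit.

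Section 7.1.2 makes two further statements on PFS. For patients who leave: "If the patient comes off study, PFS will need to be censored, but the time to first progression will be obtained during subsequent follow-up", subject to their consent. For responders who continue dosing: "In this setting, PFS will be measured in the traditional way". Neither gives a censoring date. No section sets the last tumour assessment as the PFS censoring date.

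**The concern.** One date is used for endpoints that are observed in different ways. A contact shows that a patient is alive, so last contact is a sound censoring date for survival. It does not show that the tumour has not grown by 20%; only a measurement can.

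When the last contact is not a measured visit, the time since the last measurement is credited as progression-free, and the patient stays in the PFS risk set through that time. This can happen if a patient is lost without an early termination visit, or is last seen at an unscheduled visit run to the 7.3.6 list. Some of these patients may be leaving because the disease is progressing. What is at stake is a PFS summary that is flattered by unobserved time. The safety conclusion is not at stake.

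**Working it through.** **The plan's own figure.** The only computed figure in section 10 is the upper limit on the DLT rate in 10.5. With 0 DLTs in 6 patients, the one-sided 95% exact limit is 1 − 0.05^(1/6) = 0.393, as stated. It does not involve PFS, so no choice of PFS censoring date changes it. No figure is stated for PFS.

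**How long the unobserved interval can be.** Seven business days are 9 to 11 calendar days, depending on the weekday and ignoring holidays.
- Single dose: measured on Day 0, final visit at Day 28 ± 7 business days (7.3.4). The latest final visit is 28 + 9 = Day 37 to 28 + 11 = Day 39, so the interval can approach 37 to 39 days.
- Multiple dose: the Protocol Summary and the 7.3.7 table put the final visit 21 days after the last dose, which gives up to 21 + 11 = 32 days. Section 7.3.4 says Week 21, which read literally gives up to 147 + 11 = 158 days. These passages contradict each other and must be reconciled.
- Minimum: 0 days, when the last contact is a measured visit.

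**Direction of the effect.** The plan names no PFS estimator, so assume Kaplan-Meier: S(t) is the product of (1 − d/n) over event times, with d progressions among n patients at risk. Censoring a dropout later keeps n the same or larger at each event time, so every factor stays the same or rises. With the same recorded events, last-contact censoring therefore gives an estimate equal to or above that from last-assessment censoring. The two differ only if another patient's progression is recorded after the dropout's last measurement and no later than the dropout's last contact.

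**Can that happen?** On the nominal schedule it often does not. A dropout measured on Day 0 and last contacted on Day 27 has left the risk set before a Day 28 event under either rule. The windows change this. Another patient's Week 4 visit can fall as early as 28 − 11 = Day 17 to 28 − 9 = Day 19, and the dropout's own visit can be scheduled as late as Day 37 to 39. A contact can therefore outlast another patient's recorded progression.

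**Illustration.** The documents give no dropout or progression counts, so these are assumptions: six patients; dropouts measured only on Day 0 and last contacted just after Day 28; progressions recorded on Day 28. Under last contact, n = 6 on Day 28. Under last assessment, n = 6 minus the dropouts.

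| Progressions | Dropouts | Last contact | Last assessment |
|---|---|---|---|
| 1 | 1 | 1 − 1/6 = 0.833 | 1 − 1/5 = 0.800 |
| 1 | 2 | 1 − 1/6 = 0.833 | 1 − 1/4 = 0.750 |
| 2 | 1 | 1 − 2/6 = 0.667 | 1 − 2/5 = 0.600 |
| 2 | 2 | 1 − 2/6 = 0.667 | 1 − 2/4 = 0.500 |

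**The case against.** The strongest case against is that little depends on this. PFS is not needed for the conclusion, the secondary endpoints named in 10.4.1 do not include it, no curve, median or landmark rate is planned, and all results are called preliminary. That stands, and it limits the point to a minor one.

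Second, the plan has safeguards. The early termination visit measures lesions, the single-dose table marks measurement at unscheduled visits, and 7.1.2 seeks later progression dates. Where a measurement is made at the last contact, there is no gap. But a lost patient may not attend a termination visit, the unscheduled-visit entries disagree, and later follow-up needs consent. The long-term follow-up lists survival and later therapies, with clinical response if available, but no progression date. The safeguards narrow the gap without closing it. No routine telephone follow-up is scheduled either, so contact without a visit is a possibility and not a planned event.

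Third, a reader might infer that every such dropout inflates PFS, or measure the bias by one patient's extra days. A patient measured on Day 49 and last contacted on Day 69 is credited with 69/49 = 1.41 times the observed time. That ratio is one hypothetical patient's censored duration and not a change in any estimate. If the next event is recorded on Day 70, the estimate is the same under both rules. Nor do the two additional patients in section 5.3 serve as a dropout estimate: they are replacements, and progression, which is a PFS event, is one of the reasons for replacement.

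**Conclusion.** The point holds as a minor one. The text of 10.4.1 is explicit, it covers PFS, and no other section overrides it, so unobserved time can be credited as progression-free. Given the same recorded events, the estimate is unchanged or raised. It is raised only when another patient's progression falls between a dropout's last measurement and last contact.

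In the illustration with one progression, the stated rule is higher by 0.833 − 0.800 = 0.033 with one dropout and by 0.833 − 0.750 = 0.083 with two. These figures rest on a Kaplan-Meier summary and on assumed dropout counts and dates; they are not forecasts.

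A reader might infer that the trial's findings are compromised. The documents do not support that: the feasibility criterion, the DLT limit of 0.393 and the response rate do not use this censoring rule.

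**What to change.** In 10.4.1, limit the last-contact rule to overall survival and add a PFS rule, for example: PFS is censored at the date of the last tumour assessment showing no progression, or at Day 0 if there is no assessment after baseline.

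In the same edit, reconcile 10.4.1 with 7.1.2. State whether a progression date learned after a patient comes off study counts as a PFS event or is reported separately, and say what measuring PFS in the traditional way means. Also make 7.3.6 and the 7.3.7 table agree on lesion measurement at unscheduled visits, and reconcile the timing of the multiple-dose final visit.

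The cost is a few sentences. No visit is added, and the sample size and primary endpoint do not change. Assessment dates should already be recorded, since lesion measurement is on the visit lists. The downside is slightly shorter PFS follow-up. The change also does not remove informative censoring: a patient who leaves because of unmeasured progression is still censored, only earlier.

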10.4.2 Safety Analyses

Safety endpoints will be analyzed as summary statistics during treatment and/or as change scores from baselines such as shift tables. AEs will be coded using Medical Dictionary for Regulatory Activities (MedDRA), calculated (counted once only for a given participant), presented (severity, frequency, and the relationship of AEs to study agent will be presented by System Organ Class and preferred term groupings). The information reported about each AE will be the start date, stop date, severity, relationship, outcome, and duration). AEs leading to premature discontinuation from the study and serious treatment AEs will be presented either in an independent table or a listing.

10.4.3 Baseline Descriptive Statistics

Study cohorts and groups will be compared on baseline characteristics, including demographics and laboratory measurements, using descriptive statistics.

10.4.4 Planned Interim Analyses

10.4.4.1 Safety Review

The safety analysis will be conducted on the Safety Population. The following safety parameters will be evaluated: adverse events, clinical laboratory tests, physical examinations, vital signs, ECOG performance status, ECGs, radiographic or other imaging assessments, immune safety, and immunogenicity. All safety parameters will be summarized using descriptive statistics.

- **Adverse Events**

Treatment-emergent adverse events (TEAEs) are defined as signs or symptoms that emerge during treatment or within 30 days of the last dose of Investigational Product, including those signs and symptoms that have been absent pre-treatment or that have worsened relative to the pre-treatment assessment. Any adverse event considered related to treatment will also be considered a TEAE, regardless of the elapsed time since the last dose of Investigational Product.

An immune response AE, a subset of adverse events, is defined as a clinically significant AE of any organ that is associated with Investigational Product exposure of unknown etiology and is consistent with an immune-mediated mechanism.

All AEs recorded during the study will be summarized by cohort using descriptive statistics. The incidence of TEAEs will be summarized by body system, preferred term, verbatim of adverse event, intensity (based on CTCAE Version 5.0 grade), and relationship to the Investigational Product.

- **Vital Signs**

The observed vital signs at each visit and the change from baseline to each post-baseline visit will be summarized by cohort using descriptive statistics.

- **Physical Examination**

Abnormal findings in the physical examination will be summarized by dose cohort using descriptive statistics.

- **Clinical Laboratory Tests**

Clinical laboratory test values outside the normal range and clinically significant abnormal range will be flagged in the data listing. Laboratory data will be summarized by cohort using shift tables (baseline to notable post-baseline visit). The change from baseline will be summarized using descriptive statistics.

- **ECOG**

The data observed from ECOG performance status will be summarized appropriately.

- **Other Safety Evaluations**

The results of ECGs, radiographic or other imaging assessments, immune safety tests, and immunogenicity will be summarized appropriately.

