4.2 Study Endpoints

4.2.1 Primary Endpoint

The primary endpoints of this trial will be the safety and feasibility of the treatment regimen. Safety will be reported using Common Terminology Criteria for Adverse Events (CTCAE) version 5.0. Feasibility will be defined as the ability to treat at least five of the six patients enrolled without dose-limiting toxicity (DLT).

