6.1.7 Starting Dose and Dose Escalation Schedule

The dose/lesion treated will be constant through this study: 100 µg of plasmid DNA per lesion injected at a final dose volume of 0.2 mL. However, depending on the subject, one, two, or three lesions would be injected at a time.

The subjects will receive IFx-Hu2.0 at a single time point as a monotherapy. These patients will then be observed for any dose-limiting toxicity or adverse events for up to four weeks. The maximum number of lesions to be injected in this study is three lesions.

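### The planned adverse-event tables pool the single-time-point regimen with optional repeat cycles, and toxicity over those cycles has no summary of its own

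*Combined protocol and SAP*

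**What the plan says.** The regimen is one administration, with an option to continue. Section 6.1.7 states: "The subjects will receive IFx-Hu2.0 at a single time point as a monotherapy", followed by observation for up to four weeks. Section 6.1.9 then allows further doses on a 3-week cycle. Section 4.1 ties continuation to absence of progression and section 7.1.2 to a response, in both cases at the investigator's discretion in consultation with the sponsor.

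On endpoints, section 4.2.1 says: "The primary endpoints of this trial will be the safety and feasibility of the treatment regimen". Repeat dosing appears under section 4.2.2: "Patients who consent to additional injection cycles will be observed for toxicity over time".

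On analysis:
- The safety set (section 10.3) is exemplified as "participants who took at least one dose of Investigational Product", so re-treated patients are in it.
- TEAEs (section 10.4.4.1) are "signs or symptoms that emerge during treatment or within 30 days of the last dose of Investigational Product". In addition: "Any adverse event considered related to treatment will also be considered a TEAE, regardless of the elapsed time since the last dose".
- The same section adds: "All AEs recorded during the study will be summarized by cohort using descriptive statistics".
- Section 10.4.2 counts an AE a single time per participant.

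No section defines a cohort in this one-arm study with a constant dose per lesion, and none divides the AE tables by cycle, by dose number, or at the first optional dose.

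**The concern.** Section 10.4.4.1 does not mention the optional cycles, but nothing restricts the last dose to Day 0, and the protocol summary uses the same anchor for follow-up of optional dosing. On the plain reading, a patient who continues is at risk of a TEAE for longer, and after more doses, than one who does not. Both enter one incidence figure.

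Two questions are then left without a direct answer. The first is what happens after the single administration, which is the regimen under primary assessment. The second is what repeat administration adds. The pooled incidence rises with the number of patients who continue. Continuation depends on how the patient is doing, so exposure time depends on outcome. Section 10.4.1 describes the trial as preparation for a combination study, so readers will want the two answers separately.

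**Working it through.** **1. The plan's own figure.** Section 10.5 gives a one-sided 95% exact upper limit of 0.393 for no DLTs in six patients. Solving (1 − p)^6 = 0.05 gives p = 1 − 0.05^(1/6) = 0.393, so it reproduces. The inputs are six patients and a DLT defined within its own 4-week period. The TEAE definition does not enter, so this figure and the five-of-six feasibility criterion stay as they are.

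**2. Length of the TEAE window.** Dosing days come from the sample multiple-dose schedule in section 7.3.7 (Days 0, 28 and 49), and the 30 days from section 10.4.4.1.
- Single dose: 0 + 30 = Day 30.
- Sample three-dose schedule: 49 + 30 = Day 79.
- Ratio: 79/30 = 2.63.

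The schedule is only a sample and no maximum number of cycles is given, so Day 79 is not an upper bound. Related events have no time limit in either case.

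**3. Effect on incidence.** The documents give no AE rate and no expected number of patients continuing, so both are assumed. Let q be the 30-day risk, with constant hazard. A three-dose patient has risk r = 1 − (1 − q)^(79/30). If three of six patients follow the sample schedule, the expected table incidence is (3q + 3r)/6.

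| Assumed q | r, three-dose patient | Table, three of six continue |
|---|---|---|
| 10% | 24.2% | 17.1% |
| 20% | 44.4% | 32.2% |
| 30% | 60.9% | 45.5% |

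**4. Sensitivity.**
- *Scheduled visits instead of the 30-day rule.* The comparison is Day 28 against 49 + 21 = Day 70, a ratio of 2.5. The same assumed risks over 28 days become 1 − (1 − q)^2.5 = 23%, 43% and 59%. The 21 days come from the protocol summary and the schedule table. Section 7.3.4 gives this visit as Week 21, and the passages need reconciling.
- *Risk per dose instead of per day.* With an independent risk p at each dose, three doses give 1 − (1 − p)^3 = 27.1%, 48.8% and 65.7% for p = 10%, 20% and 30%. If three of six take three doses, the table averages about 19%, 34% and 48%.

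The size is similar under each version.

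**5. Can the split be recovered?** Section 10.4.2 reports start and stop dates for each AE, so onset can be placed before or after a second dose. Worsening is less certain. Section 8.1.1 records an ongoing or intermittent event once at its worst grade, whereas section 8.3 asks for each change in severity and each episode. Under the first rule alone, an event that is mild after dose 1 and severe after dose 3 appears once, at the later grade.

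**The case against.** The case for leaving the plan alone has several parts.

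- **The decision rule is safe.** A reader might infer that pooling contaminates the primary safety conclusion as a whole. It does not: DLTs carry their own 4-week limit, and only the descriptive safety summaries are touched. This stands in full.
- **Section 4.2.2 is thin.** A reader might infer that a fully specified repeat-dose toxicity endpoint has been left out. The documents do not support that. It is one sentence without a metric, and neither section 3.2 nor the secondary endpoints in section 10.4.1 list it. What remains is that the plan mentions the item and provides no summary for it.
- **An all-exposure table fits the objective.** Section 3.1 speaks of vaccination as monotherapy without a single-dose limit. That justifies keeping the pooled table, but not having it as the only one.
- **Cohort might mean single- versus multiple-dose patients.** It might, since section 7.3.7 sets out both scenarios, but no text says so. The defect shown is an undefined term, not a grouping known to be wrong. Such a grouping would also still mix the first and later doses of the same patient.
- **Six patients can be read from a listing.** Largely true, given the reported dates. The information is not lost. The planned incidence figures simply do not show it.
- **The 24/44/61% figures are an extreme.** They describe one patient on a sample schedule, under assumed risks. The table-level figures are the fairer measure.

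**Conclusion.** The concern holds for the descriptive safety tables. As planned, TEAE incidence pools first-dose and repeat-dose experience over windows whose length depends on who continues, and toxicity over additional cycles has no planned summary. The table-level effect, if half the patients continue on the sample schedule, is roughly a 1.5- to 1.7-fold rise (45.5/30 to 17.1/10). This rests on assumed AE risks, a constant hazard and an assumed number continuing, and there is no effect if nobody is re-dosed. The change is worth making because the tables report on the trial's primary safety question and the data are already collected. It does not call into question the DLT/feasibility criterion or the stated precision.

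**What to change.** In section 10.4.4.1:

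1. Add a first-dose-period AE table for all treated patients, with onset from Day 0 up to the first optional dose. For patients not re-dosed, keep the existing 30-day rule and retain later related events, so that none drops out.
2. Add a separate table, or a listing given six patients, of AEs with onset or worsening after the first optional dose, labelled as the section 4.2.2 summary. Give the number of patients exposed and their follow-up time as denominators. Do not stratify further by number of doses, because the cells would hold one or two patients.
3. Report follow-up time for the first-dose period too. It ends at the second dose, and the Day 28 ± 7 business days window lets that fall between about Day 17 and Day 39 (weekday starts, no holidays).
4. Keep the pooled table as a supplement.
5. Define cohort to match this split, or delete the term.
6. Reconcile the recording rules in sections 8.1.1 and 8.3, so that worsening after re-dosing can be identified.

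The cost is one more small descriptive table with sparse cells. No new visits or assessments are needed, and the sample-size statement is unchanged.
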